- Women with IC/BPS who have a score of ≥ 6 on either index (problem or symptom index) of the O'Leary-Sant questionnaire who have selected bladder instillations as part of their IC/BPS treatment
- Suitability for follow-up

Exclusion Criteria:

- Contraindications to the ingredients used in the bladder instillations
 - In particular: allergy to ingredients
 - Diagnosis of idiopathic thrombocytopenic purpura
- Does not desire to undergo bladder instillation therapy or unwilling to undergo bladder instillation therapy on schedule mandated by study
- Have a known alternative diagnosis explaining bladder pain symptoms that would preclude the diagnosis of IC/BPS (e.g. radiation cystitis, active urinary tract infection with bacteria or fungus treated within last 2 weeks or diagnosed at index visit, bladder injury or trauma within the last 30 days)
- Inability to speak or read English
- Bladder instillation within the past 4 weeks

Study Title: Randomized controlled trial comparing two different bladder instillation treatments for interstitial cystitis/bladder pain syndrome.

Interventions:

Eligible patients will be randomized by a research statistician to one of two possible interventions:

1. Bladder instillation with Kenalog
2. Bladder instillation without Kenalog

The randomization sequence, generated by a statistician that is uninvolved in patient recruitment, will be in randomly alternating block sizes of 6-10 with a 1:1 distribution in each block. The sequence will be attached by a research medical assistant, also uninvolved in patient selection and recruitment, to the numbering of otherwise unmarked, identical syringes containing either a bladder instillation mixture with Kenalog or a mixture without Kenalog. The appearance of the syringes will be identical in every way except for the patient number on the labelling. The study investigators recruiting, treating, or assessing the patient during the study will not be aware of the patient's randomization, and the randomization sequence will not be opened until the last patient is through with the study unless an adverse event mandates.

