All study bladder instillation mixture will be drawn up in syringes, randomized, and dispensed (given to provider) by one of the medical assistants. The providers will be blinded to the study mixture and will perform the bladder instillations. The bladder instillation ingredients will be prepared in a standardized fashion by a trained medical assistant. The patients will undergo bladder instillations using a standardized technique by a physician or nurse practitioner. The medical practitioner will swab the external urethral meatus with betadine (or other appropriate cleansing agent if patient has an iodine allergy) and then instill approximately 5 mL of 1% viscous lidocaine in the urethra, letting the viscous lidocaine sit for 1 to 10 minutes. A pediatric (8 French) straight-tip catheter will be inserted to drain the bladder and collect a urine specimen for culture if indicated. After the bladder is drained, the bladder will be instilled with either a mixture of triamcinolone acetonide (1 vial, 40 milligrams (mg)/1 milliliters (mL)), heparin (10,000 units), 2% viscous lidocaine (10 mL), 8.4% sodium bicarbonate (15 mL of 1 mEq/mL), and 0.5% bupivacaine (10 mL of 5 mg/mL). After the instillation, the women will lay supine or move from supine to lateral positions intermittently for 20-30 minutes. They will then urinate the instillation. If a patient has previously demonstrated the ability to urinate without difficulty following an instillation, she may depart the office after 20-30 min and urinate the instillation in a more private, non-office setting.

If patients have a reaction to the bladder instillation or desire to stop the instillations, they may do so. Participants will be permitted to obtain any relevant concomitant care and interventions during the trial.

Outcomes

All outcome measures will be collected at 3 weeks into the bladder instillation schedule and again at the completion of the bladder instillations (6 weeks into study participation).

Study Title: Randomized controlled trial comparing two different bladder instillation treatments for interstitial cystitis/bladder pain syndrome.

Primary Outcome:

1. Treatment response as measured by the score of the O'Leary-Sant questionnaire [16,17] as compared between study groups at completion of the bladder instillations.

Secondary Outcomes:

1. O'Leary-Sant subscores (problem and symptom index) at the completion of treatment

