2. Change in O'Leary-Sant total scores and subscores (problem and symptom indices scores) from baseline to last collected measure
3. Pelvic pain and urgency/frequency (PUF) questionnaire [18]
4. Overactive Bladder Questionnaire (OABq) [19]
5. Pelvic floor distress inventory (PFDI) [20]
6. Sexual function measured by the Pelvic Organ Prolapse Incontinence Sexual Questionnaire, IUGA-Revised (PISQ-IR) questionnaire [21-23]
7. Visual Analogue Scale (VAS) for pain as measured on marking on 10-centimeter (cm) ruler (measured in cm, 0= no pain and 10= most severe pain possible)
8. Prevalence and nature of adverse events related to study medications
9. The prevalence of notable OAB symptoms in the study population and in the different study groups, as defined by OABq score ≥ 8
10. The prevalence of concurrent pain or irritative organ disorders (irritable bowel syndrome, fibromyalgia, chronic pain, chronic pelvic pain, vulvodynia, anxiety, depression, chronic fatigue syndrome) in the study population and in the different study groups
11. Perform cost-analysis of two treatment groups

Participant timeline:

Upon recruitment, women will complete questionnaires (Figure 1) about their characteristics and health history, presence or absence and number of other pain syndromes related to IC/BPS (irritable bowel syndrome, fibromyalgia, chronic pain, chronic pelvic pain, vulvodynia, anxiety, depression, chronic fatigue syndrome), and complete the following reliable, validated questionnaires as follows:

- (1) O'Leary-Sant questionnaire (problem and symptom index scores) [16,17]
- (2) Pelvic pain and urgency/frequency (PUF) questionnaire [18]
- (3) Overactive Bladder Questionnaire (OABq) [19]
- (4) Pelvic floor distress inventory (PFDI) [20]
- (5) Sexual function measured by the Pelvic Organ Prolapse Incontinence Sexual Questionnaire, IUGA-Revised (PISQ-IR) questionnaire [21-23]
- (6) Visual Analogue Scale (VAS) for pain as measured on marking on 10-centimeter (cm) ruler (measured in cm, 0= no pain and 10= most severe pain possible)

Study Title: Randomized controlled trial comparing two different bladder instillation treatments for interstitial cystitis/bladder pain syndrome.

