Bladder instillation will be performed weekly with the same mixture that the patient was randomized to (mixture with or without Kenalog) and for 6 weeks. Symptom questionnaires will be given at baseline, 3 weeks, and 6 weeks of treatment. If the patient misses a study appointment, she will be called by telephone and queried about side effects and if appropriate, re-scheduled for an appointment.

We plan to recruit patients from January 2019 until July 2020. Patient follow up will be completed by September 2020. As bladder instillations are commonly performed and considered low risk, no interim analysis will be performed. Urinary tract infection will not be considered an adverse event related to study drug but will be monitored in data collection.

Sample size

Sample size calculation was based on the primary outcome, the O'Leary-Sant score on the final day of bladder instillation treatment as compared between the two treatment groups. Based on previous studies, patients have a baseline IC/BPS score following standard medical treatment of approximately 24 ± 5.6 points.[16,17] A 4.03 point decrease from baseline on the O'Leary-Sant questionnaire corresponds with at least a 50% perceived improvement in the patient's disease.[24] We believe this level of difference between the groups in the final O'Leary-Sant scores would be clinically significant. We want 80% power to detect a 4.03 point decrease from a baseline mean score of 24 (expected score in the bladder instillation without Kenalog group after treatment) with a standard deviation ≤ 5.6 points (alpha 0.05) with a 2-sided t-test. The G*Power sample size calculator was used for the power calculations (<https://www.stat.ubc.ca/~rollin/stats/ssize/n2.html>) and these calculations were confirmed for accuracy by a University of Louisville biostatistician. The resulting sample size was $n= 32$ for each group for a total of 64 enrolled patients. Accounting for a 20% dropout in the study, this would translate to a sample size of 80 patients enrolled with a goal of 40 per group.

Recruitment

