The patients, once consented, will be randomly assign to a treatment group by using the randomization sequence that was created by an uninvolved statistician. The patients will use their SIDNs for the remainder of the study. They are blinded to treatment because the study medications all look the same except for the syringe labeling with the patient's SIDN. All patients will otherwise receive the same treatment and care.

The investigators are blinded because they are not privy to the bladder instillation mixture that the patient was assigned to and all patients are otherwise treated and assessed the same.

Unblinding (unmasking)

Should unblinding be warranted such as in exceptional circumstances when knowledge of the actual treatment is absolutely essential for further management of the patient, the ULH biostatistician who has access to patient allocation, will be contacted to disclose to the principal investigator (PI) which treatment group the affected participant was assigned. The incident will be submitted on a case report form.

Methods: Data collection, management, and analysis

Study Title: Randomized controlled trial comparing two different bladder instillation treatments for interstitial cystitis/bladder pain syndrome.

Data collection methods

All information will be obtained directly from questionnaires completed by the patient at the initial study visit, from contact points during study visits at which bladder instillations, are being performed, or at the end of the study at the 6th bladder instillation. The patients will undergo bladder instillations at the University of Louisville Female Pelvic Medicine clinics either at the Spring Clinic location or the HCOC building, and data from validated questionnaires and medication compliance worksheets will be collected on paper at the appropriate time point. Data will be extracted and entered into a RedCap or password-protected Excel spreadsheet as outlined below. No data will be extracted from the patient's medical record or HCOC AllScripts electronic medical record system for this study; all data will be collected directly via study questionnaires and data report sheets designed for use in this study.

Retention and follow-up

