We plan to query adverse events or side effects at each study visit. We offer appointments three days a week to allow for optimal scheduling and will call patients if they are unable to make their follow up visit to ask about medication side effects as well as reschedule them for another appointment time. They will be given written and verbal instructions on what to do in the event of side effects or adverse events to increase the likelihood of them presenting in person and communicating with their physician and/or study investigators about any issues. Patients will be allowed to submit their interval and end-of-study questionnaires during their appointment visits.

Data Management

Data collection form: See below and Appendix A

The following information will be collected directly from study questionnaires and entered into an encrypted excel spreadsheet:

- Study ID number (SIDN)
- Name
- Date of birth
- Age
- Race/ethnicity
- Contact information
- Emergency contact information (if patient willing to provide)
- Social security number (SSN)
- Weight
- Body mass index (BMI)
- Smoking status
- Gravidity
- Parity

Study Title: Randomized controlled trial comparing two different bladder instillation treatments for interstitial cystitis/bladder pain syndrome.

- Reason for visit
- Prior pelvic reconstructive surgery
- Medical history, specifically history of: irritable bowel syndrome, fibromyalgia, chronic pain, chronic pelvic pain, vulvodynia, anxiety, depression, chronic fatigue syndrome
- Charleston comorbidity index[25]
- O'Leary-Sant questionnaire (problem and symptom index scores)[16,17]
- Pelvic pain and urgency/frequency (PUF) questionnaire[18]
- Overactive Bladder Questionnaire (OABq)[19]
- Pelvic floor distress inventory (PFDI)[20]
- Sexual function measured by the Pelvic Organ Prolapse Incontinence Sexual Questionnaire, IUGA-Revised (PISQ-IR) questionnaire[21-23]
- Visual Analogue Scale (VAS) for pain
- Timing and nature of adverse events during the study, regardless of suspected or known relationship to study medication

Data Handling/Storage:

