All identifying information and data collected during the course of this study will be kept secure and strictly confidential. All data will be stored electronically on a password protected, encrypted laptop in the possession of the study investigator. Risks for breaches of confidentiality will be minimized by entering data from the medical record to a password protected, encrypted computer database which will have limited access to the PI.

The patient's unique study ID will be used for storage, analysis and publication.

Paper data collections forms will be utilized and data will be entered from the paper data form by a study investigator into either a RedCap database or an encrypted, password protected laptop or computer Excel database. These data forms will be housed in a locked file cabinet in the Division of Female Pelvic Medicine and Reconstruction office in a locked cabinet with restricted access.

Data Analysis and Statistical Methods:

The data will be analyzed in consultation with a department-committed biostatistician utilizing SPSS statistical software. Categorical variables (e.g. 'yes" to certain questions on the PFDI) will be compared using chi-square tests (or Fisher's exact test when appropriate). Continuous variables (such as primary outcome) will be compared using t-tests, and changes in continuous outcomes over time (e.g. change from baseline to 8-week O'Leary-Sant score) will be compared with paired t-tests. A regression analysis will be performed to determine the impact of various relevant cofactors (e.g. patient age, presence of other chronic disorders, level of OAB symptoms) on the relationship between group assignment and treatment outcomes.

We will perform an intention-to-treat analysis by the assigned study groups for the initial analysis, comparing women who followed up at the completion of the study (6-week outcomes) between the study groups (bladder instillations with and without Kenalog) as

Study Title: Randomized controlled trial comparing two different bladder instillation treatments for interstitial cystitis/bladder pain syndrome.
assigned. We will also perform a per-protocol analysis, comparing women in the bladder instillation with Kenalog who had at least 4 bladder instillation treatments to the group that had bladder instillations without Kenalog. Lastly, we will perform two types of sensitivity analysis:

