As this study has minimal risk, a Data Safety Monitoring Board (DSMB) is not required. However, the study participants will be given numbers to reach the principal investigator, clinic, or after-hours answering service should they experience any side effects or adverse events related to the study. They will be advised to seek care from their doctor for medical advice related or unrelated to the study, and the study investigators will alert the University of Louisville IRB apprised of all adverse events experienced by trial patients, regardless of severity or clinical belief of relation to the study drug. If an adverse event is sufficiently severe enough to merit stopping the study drug temporarily or permanently, we will work in collaboration with the IRB to determine if patient randomization should be revealed. This determination will come after the drug has been stopped and appropriate medical attention given to the patient. Serious, drug-related adverse events will be those that require intravenous medication, hospital admission, or procedural intervention and are considered to be directly associated with study treatment. If $\geq 25\%$ of patients have experienced an adverse event thought to be related to the study drug or if $\geq 10\%$ of patients have experienced a serious adverse event related to the study drug, the study will be terminated early.

Harms:

Adverse event and unintended effects of trial interventions or trial conduct will be managed by a Research Nurse, and the investigators. Such information will be both solicited and participants will be encouraged to spontaneously report such effects. The research team will closely monitor data collection and assure confidentiality at every point during this study. The IRB and appropriate hospital research office will be notified immediately of any adverse events, including security breaches of the data, or UPIRTSOs, whether expected or unexpected. Participants will discontinue the products if they have an allergic reaction to the medication or any of its components. The worse anticipated adverse reaction is discomfort with bladder instillation which would be monitored, recorded, and responded to by either our Research Nurse or the patient's chosen provider.

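### UTI is ruled unrelated to study drug in advance, so on the natural reading it is left out of the only adverse-event outcome, and no by-arm UTI summary is prespecified

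*Combined protocol and SAP*

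**What the plan says.** Four parts of the combined protocol and SAP bear on this.

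- **Attribution.** Participant timeline: "Urinary tract infection will not be considered an adverse event related to study drug but will be monitored in data collection".
- **Outcome.** Secondary Outcomes, item 8, is the only adverse-event outcome: "Prevalence and nature of adverse events related to study medications". Items 9 and 10 ask for prevalence in each study group; item 8 does not.
- **Collection.** Data Management lists "Timing and nature of adverse events during the study, regardless of suspected or known relationship to study medication". Data monitoring says that the IRB will hear of all adverse events, "regardless of severity or clinical belief of relation to the study drug".
- **Analysis.** Data Analysis and Statistical Methods has one general sentence: categorical variables "will be compared using chi-square tests", or Fisher's exact test where suitable. It names neither UTI nor adverse events, and neither do the sensitivity and secondary analyses that follow.

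The arms differ by the presence of Kenalog. The Interventions section describes one catheter step for everyone: "A pediatric (8 French) straight-tip catheter will be inserted to drain the bladder and collect a urine specimen for culture if indicated". The Blinding section adds: "All patients will otherwise receive the same treatment and care".

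**The concern.** Whether UTI is more frequent when a steroid is put into the bladder is a question that this randomised trial can address. The attribution rule answers it before any data exist. Outcome 8 then filters on attribution, so a reader of that outcome could not tell whether UTI was equally common in the two arms.

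The count also helps in reading the symptom scores. The Exclusion Criteria list, among alternative diagnoses that explain bladder pain, "active urinary tract infection with bacteria or fungus treated within last 2 weeks or diagnosed at index visit". On the plan's own terms, then, UTI can produce the symptoms being scored, and a by-arm count at week 6 is useful context.

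What is at stake is the completeness of planned safety reporting. A UTI table made after unblinding would be unplanned, with its definition chosen when the results could be seen.

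**Working it through.** **1. The plan's own figures.** No stated figure concerns UTI. The sample size sets the denominators: a difference of 4.03, SD 5.6, two-sided alpha 0.05 and 80% power give 31.3 per group by t-test, rounded up to 32. Then 64 / (1 − 0.20) = 80 enrolled, or 40 per arm. Both figures reproduce.

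**2. Following the rule through.** Every UTI is classed as not related to *study drug* (Participant timeline). Outcome 8 counts events related to *study medications*. If the two terms are the same, outcome 8 contains 0 v 0 UTIs for any true split. If they differ, the plan does not settle whether UTI enters outcome 8.

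**3. What a by-arm table would show.** The documents give no UTI rates, so the counts below are assumptions at 40 per arm. The interval is the Newcombe score interval, built from the Wilson limits (l, u) of each arm:

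- lower = d − √[(p₁ − l₁)² + (u₂ − p₂)²]
- upper = d + √[(u₁ − p₁)² + (p₂ − l₂)²]

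For 12/40 with Kenalog v 4/40 without, the Wilson limits are 0.1807 to 0.4543 and 0.0396 to 0.2305. With d = 0.200:

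- lower = 0.200 − √(0.1193² + 0.1305²) = 0.023
- upper = 0.200 + √(0.1543² + 0.0604²) = 0.366

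| Kenalog v control (of 40) | Risk difference | 95% CI | Fisher p | UTIs in outcome 8 |
|---|---|---|---|---|
| 4 v 4 | 0.000 | −0.144 to 0.144 | 1.00 | 0 v 0 |
| 8 v 4 | 0.100 | −0.061 to 0.259 | 0.348 | 0 v 0 |
| 12 v 4 | 0.200 | 0.023 to 0.366 | 0.048 | 0 v 0 |

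**4. How large a difference could be distinguished.** This is the smallest Kenalog count whose interval excludes zero:

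| Control (of 40) | Kenalog (of 40) | Risk difference | 95% CI |
|---|---|---|---|
| 2 | 8 | 0.150 | 0.001 to 0.302 |
| 4 | 11 | 0.175 | 0.002 to 0.340 |
| 6 | 14 | 0.200 | 0.009 to 0.374 |
| 8 | 17 | 0.225 | 0.022 to 0.405 |

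Fisher's test needs one more event each time (9, 12, 15 and 18); for 11 v 4, p = 0.083.

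**5. Effect of dropout.** For assumed rates of 10% v 30%, the simple half-width is 1.96 × √[(0.09 + 0.21)/n]. That is 0.170 at n = 40 and 0.190 at n = 32, the number left after the planned 20% dropout.

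**The case against.** The strongest reply is that nothing is lost. UTI is monitored, all adverse events are recorded whatever their cause, the IRB sees them all, and the general chi-square sentence would permit a comparison. Since every woman is catheterised at each instillation, treating UTI as a procedural event and tracking it separately is defensible. Most secondary outcomes have no more specific an analysis than this one, and the trial is too small to show anything but a large UTI difference.

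Much of this stands. A reader might infer that the plan hides UTI, fails to collect it or forbids comparing it. The documents support none of these: the rule settles attribution only. A reader might also infer that UTI cannot enter outcome 8 under any reading. That too goes beyond the text, because *study drug* is undefined and is not expressly equated with *study medications*.

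One part of the reply does not stand. For other secondary outcomes the general analysis sentence leaves detail open; here a stated rule, followed as written, removes an event from the only safety outcome. A shared catheter step is a reason to rely on the randomised contrast, since it gives both arms the same background risk per instillation. IRB notification is not a comparison between arms.

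**Conclusion.** The point holds as a gap in prespecified safety reporting, not in data collection. It rests on reading *study drug* and *study medications* as the same thing. On that reading outcome 8 shows no UTI in either arm, even if the counts were, say, 12 and 4 of 40.

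The size of any real UTI difference is unknown, since all rates here are assumed. With 40 per arm and control counts of 2 to 8, only differences of 15 to 22.5 points would give an interval excluding zero, and fewer women observed would widen the intervals. The tables would therefore be descriptive.

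A reader might go further and infer that unreported UTIs bias the week-6 O'Leary-Sant comparison. The documents do not support that: they give no UTI rate and no sign of an imbalance, and listing UTI as an alternative cause of bladder pain shows only that the count is worth seeing.

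Separately, the terms do not match across sections. The attribution rule and the two study-termination thresholds in Data monitoring refer to *study drug*. The definition of serious events there refers to *study treatment*, the individual stopping criteria under Harms refer to *the bladder instillations*, and outcome 8 to *study medications*. Read literally, a UTI counts toward neither termination threshold, while its status under the other terms is unclear. These passages must be reconciled.

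**What to change.** Do not use the advance attribution to leave UTI out of safety reporting. Add two descriptive tables by randomised arm, in women who received at least one instillation:

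1. any UTI as recorded on study forms, under one definition and observation window fixed before unblinding;
2. all adverse events regardless of attribution.

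For each, give the number of women with an event, the risk difference and a 95% score (Newcombe) interval, with no significance claim. Show the number of instillations received by arm alongside. Outcome 8 can stay as a separate related-event row. Report culture status only where a culture was taken and the result is already on study forms: cultures are taken only when indicated, and Data collection methods rules out extraction from the medical record, so a new culture field could need a results source and a follow-up step.

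The sponsor should also reconcile the four terms named above; which meaning applies is the sponsor's choice.

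**Cost.** Wording and two tables from data that the plan already collects, with no change to the sample size. Whether the Appendix I worksheet has a distinct UTI entry cannot be seen from the documents. The downsides are that reported event rates will look higher in both arms, uncultured UTIs are less certain, women who stop early are observed for less time, and a UTI after the sixth instillation visit may be missed.

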Small studies (<40 patients) have shown improvement of IC/BPS symptoms in patients with use of steroids. However, no previously published studies have evaluated the efficacy of Kenalog in bladder instillations using this larger size study design. The proposed research is innovative: (1) it builds upon the current evidence that IC/BPS is a systemic chronic pain condition that may respond to steroid medications and (2) it is a bigger and more rigorous study than previously published studies evaluating the role of steroids in bladder instillation treatment of IC/BPS in women. Based on the results of this study, new and improved therapeutic options will be attainable for IC/BPS and other pelvic floor disorders.

Trial design:

This will be a single center, randomized, double-blind, controlled trial. Women will be recruited from a subspecialty clinic at the University of Louisville and be eligible for participation if they have selected a course of bladder instillation treatments with their

Study Title: Randomized controlled trial comparing two different bladder instillation treatments for interstitial cystitis/bladder pain syndrome.
physician as therapy for a diagnosis of IC/BPS. Eligible consenting participants will undergo randomization with equal probability of assignment to one of the two groups: (1) bladder instillation with Kenalog (2) bladder instillation without Kenalog. They will undergo weekly bladder instillations for 6 weeks. Patients and providers will be blinded to study allocation. Clinical outcomes will be assessed at 3 weeks into treatment (3 weeks into bladder instillations) and at the end of treatment (6 weeks).

Methods and Procedures: Participants, interventions, and outcomes

Study setting:

Subjects will be recruited from the ULP Female Pelvic Medicine and Reconstructive Surgery (FPMRS) practice at the University of Louisville Health Care Outpatient Center (HCOC) and the Springs Medical Center.

- Study Sites:**

- University Health Care Outpatient Center (HCOC)
 - Springs Medical Center

Eligibility criteria:

Eligible women will be offered participation in the trial by clinic providers and will sign an informed consent with the study investigators prior to completing further study materials or receiving any interventions for IC/BPS.

Inclusion Criteria:

- Age \geq 18-years old

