Prior to offering enrollment in the study, the patient must desire bladder instillation therapy for treatment of her IC/BPS symptoms. The standard practice of bladder instillations is to cleanse the external urethral meatus with betadine or another appropriate cleansing solution. This, as well as the insertion of a small bladder catheter, can sometimes be uncomfortable for patients. Sometimes the instillation solution can be uncomfortable for

Study Title: Randomized controlled trial comparing two different bladder instillation treatments for interstitial cystitis/bladder pain syndrome.

patients due their IC/BPS symptoms and the expansion of their bladders. These potential risks and discomforts are not over and above that experienced in a standard visit to this clinical service. That being said, there may be ways to reduce the occasional discomfort of undergoing a bladder instillations, such as using topical lidocaine gel for insertion of the bladder catheter and instilling the solution into the bladder slowly. Another potential risk is an allergic reaction to the ingredients in the bladder instillations. Although women with known hypersensitivity will be excluded, women may have unknown or new sensitivity to the medications. These are highly unlikely to be serious and are reversible on stopping use of medication. Patients will have the study personnel's contact information should they develop any adverse events prior to their weekly visit and need medical attention.

Methods: Monitoring

Data monitoring:

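### No adverse-event query is scheduled after the last instillation, so one of a completer's six instillations has no solicited safety follow-up

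*Combined protocol and SAP*

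**What the plan says.** The schedule is stated under Trial design: "They will undergo weekly bladder instillations for 6 weeks". Three provisions govern when adverse events are actively asked about.

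- **Retention and follow-up:** "We plan to query adverse events or side effects at each study visit".
- **Participant timeline:** "If the patient misses a study appointment, she will be called by telephone and queried about side effects". Retention and follow-up repeats this call, again only for a visit the woman cannot make.
- **Data collection methods:** the last source of information is the end of the study, placed "or at the end of the study at the 6th bladder instillation". The same section rules out extraction from the medical record.

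The Sample size section agrees on timing. It defines the primary outcome as "the O'Leary-Sant score on the final day of bladder instillation treatment as compared between the two treatment groups". No later visit, call or questionnaire is listed, and Ancillary and post-trial care plans none.

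Women can also report events themselves. Retention and follow-up promises written and verbal instructions, Data monitoring and Harms give telephone numbers and encourage spontaneous reports, and Potential Risks offers contact details "should they develop any adverse events prior to their weekly visit and need medical attention".

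The adverse-event record feeds secondary outcome 8 (events related to study medication) and the two early-termination rules under Data monitoring (25% of patients with a related event, 10% with a serious related event). Participant timeline states that urinary tract infection is not counted as related to study drug but is monitored.

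**The concern.** Asking each woman about the week since her previous instillation gives uniform follow-up for the first five. The sixth is given on the day the study ends for her, so the method of collection changes from active to passive at the last exposure. That visit itself may show little of what follows: under Interventions, a woman who has already shown she can void without difficulty may leave after 20 to 30 minutes.

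An event that begins after she leaves enters the dataset only if she reports it unprompted. The plan does not say until when such reports are accepted or how they are recorded. Three things could be understated: secondary outcome 8, the running counts for the termination rules while later women are still being enrolled and treated, and urinary tract infection after the last catheterisation.

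**Working it through.** **The plan's own figure.** The 64 and 80 used below come from the Sample size section. With a difference of 4.03, SD 5.6, two-sided alpha 0.05 and 80% power, a two-sample t-test needs 31.3 per group, so 32, or 64 in total. Allowing for 20% dropout, 64 / (1 − 0.20) = 80. The stated figures reproduce. The present point does not depend on them beyond these counts.

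**Which instillations are followed by a scheduled query.** With visits one week apart:

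- Instillations 1 to 5: a query at the next visit, about 7 days later, or a call if that visit is missed.
- Instillation 6: no later visit, and so no missed visit to prompt a call.

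For a completer, 5 of 6 post-instillation intervals end in a scheduled query and 1 does not: 1/6 = 16.7%. With 64 completers this is 64 of 64 × 6 = 384 instillations. If all 80 complete, it is 80 of 80 × 6 = 480.

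**Illustrative size.** The documents give no event rate per instillation, so the risk q is an assumption, shown over a range. Assume that q is equal and independent across instillations, that every event begins after the woman leaves the visit, and that nobody reports spontaneously. A woman is then missed if her only event follows the 6th instillation:

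expected number missed = 80 × [(1 − q)^5 − (1 − q)^6] = 80 × q × (1 − q)^5

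| Assumed q | With an event, six intervals | Seen, five intervals | Missed of 80 |
|---|---|---|---|
| 1% | 5.85% | 4.90% | 0.8 |
| 2% | 11.42% | 9.61% | 1.4 |
| 3% | 16.70% | 14.13% | 2.1 |
| 5% | 26.49% | 22.62% | 3.1 |

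With 64 completers the missed counts scale by 64/80 = 0.8, giving about 0.6 at 1% and 2.5 at 5%. Spontaneous reports would lower all of these.

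**Timing check.** If the first instillation is at week 0, the 6th falls at week 5, and a separate 6-week assessment could come a week later and act as the missing query. The text does not support that reading, because Sample size and Data collection methods tie the final assessment to the last instillation. Data Analysis and Statistical Methods adds a further time point, "change from baseline to 8-week O'Leary-Sant score", for which no visit is scheduled.

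**Calendar check for a 7-day call.** Recruitment runs to July 2020 and follow-up ends by September 2020. A woman starting on 31 July 2020 has her 6th instillation on 4 September (35 days later) or 11 September (42 days later). Seven days after that is 11 or 18 September, inside the stated period.

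**The case against.** The strongest reply is that spontaneous reporting stays open. The instructions and telephone numbers in Retention and follow-up, Data monitoring and Harms carry no end date, and serious events, defined by intravenous medication, admission or a procedure, are the ones a woman is most likely to report. The gap is identical in both arms, the primary outcome is untouched, and the protocol regards the study as minimal risk. All of this stands. It limits the size of the problem, but an unprompted report is not equivalent to the query that follows the other five instillations.

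A reader might infer more than the documents support, in four ways.

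- **A four-week safety window.** The exclusion criterion "Bladder instillation within the past 4 weeks" might be read as one. It is an eligibility criterion given without a reason, and the 30-day exclusion concerns bladder injury or trauma. Neither defines how long an instillation matters for safety.
- **Termination thresholds evaded.** Under the same assumptions, the true and solicited rates fall on opposite sides of 25% only for q between about 4.7% and 5.6%, and of 10% only for q between about 1.7% and 2.1%. The 10% rule also counts serious related events only. No document supports risks in those ranges.
- **Infection missing from outcome 8.** Urinary tract infection is expressly not counted as related to study drug, so a late one affects only its separate monitoring.
- **A hidden cumulative steroid effect.** Effects building up over instillations 1 to 5 are asked about at visits 2 to 6, and the documents give no data on delayed or cumulative effects.

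**Conclusion.** The point holds as a gap in solicited collection: on the current text, a completer's 6th instillation, 16.7% of her instillations, is followed by no scheduled adverse-event query. That rests on reading the end of the study as the day of the 6th instillation, which two sections support. The effect is a possible undercount of secondary outcome 8, of the termination-rule counts and of monitored urinary tract infections. The illustration puts it at about 0.8 to 3.1 of 80 women for assumed risks of 1% to 5% per instillation, before any spontaneous reports. Because the gap is common to both arms, the between-arm comparison is biased only if late events differ by arm. The documents do not support a claim that a termination rule would fail to trigger, or that follow-up must last four weeks. This is a minor improvement.

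**What to change.** Add one scripted safety call about 7 days after each woman's last instillation, whether that is the 6th or an earlier one. Record it on the Appendix I worksheet, and define the adverse-event window as first instillation to that call. The Confidentiality section has the key linking identities to study numbers destroyed once data are collected and contact is no longer needed; state that it is kept until the last call is done. Reconcile the 6-week and 8-week time points so that the final contact is unambiguous.

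The cost is protocol wording and one short call per woman, at most 80 calls, using the telephone procedure already planned for missed visits. The sample size does not change, and the calls fit within the stated September 2020 end of follow-up.
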